6.4.3 Anatomical MRI Analysis

All scans will be analyzed blind to diagnosis, age, and gender. Datasets with significant motion artifact during acquisition will have been re-acquired in the same imaging session based on real-time evaluation of imaging data and decisions made by Dr.

[name]. See figures 5a/b for example of significant motion artifact subject to reacquisition.

[figure not shown]

Figure 5A/B: Examples of T1-weighted image acquisition data from children without head injury. Panel on the left is an example of good quality T1-weighted data. Panel on the right is an example of poor quality T1-weighted data requiring re-acquisition in the same imaging session due to signs of motion artifact (e.g. ringing).

6.4.4 Freesurfer Analyses of Cortical and Subcortical Volume

For each participant, the 3D isotropic MPRAGE data is processed via the Freesurfer v5.0.0 (www.surfer.nmr.mgh.harvard.edu) image processing stream (recon-all –all). Each brain is skull-stripped and segmented into 3 classes of voxels: gray matter, white matter, and cerebrospinal fluid (Dale & Sereno, 1993; Dale et al., 1999). Subsequently, the cortex is parcellated for individual gyri yielding morphometric measures of volume within each gyrus (Fischl & Dale, 2000). Once data sets have completed the Freesurfer pipeline, the color-coded segmentation maps are visually reviewed using Freesurfer'sTkmedit viewer (Figure 6a). Inaccurate boundary delineations of non-cortical structures and white matter are manually edited and the data re-processed via the second and third stages of the Freesurfer pipeline. Color-coded cortical parcellation maps (Figures 6b and 6c) will also be reviewed via Freesurfer's Tksurfer viewer for any inaccuracies that require editing. Quantitative non-cortical volumes are extracted from the aseg.stats file; surface-based cortical data (e.g. volume) are extracted from the ?h.aparc.annot files.

Figures 6 A/B/C: Example segmentation of subcortical structures and parcellation of cortical gyri based on delimiting sulci. Panel on the level demonstrates volume-based subcortical segmentation of subcortical GM structures. Panels on the right demonstrate surface-based color-coded parcellation of cortical gyri from lateral and medial views of the left hemisphere.

6.4.5 DTI Processing and Analysis

DTI data will be reviewed for image quality during acquisition and re-acquired in the same imaging session based on real-time evaluation of imaging data and decisions made by [name]. The isotropic 32-direction DTI dataset will be processed and analyzed using FSL v4.1.7 (FMRIB's Software Library, www.fmrib/ox.ac.uk/fsl). Minor head motion and eddy currents will be corrected with the Eddy Current Correction tool in FSL's Diffusion Toolbox v2.0. FSL's FUGUE module will be used to unwarp geometric distortions in the EPI-based DTI dataset with the gradient echo field map, correcting for EPI-related distortions in the DTI dataset (particularly fronto-orbital susceptibility regions) to improve co-registration with T1 structural images. Skull-stripping and removal of non-brain tissue is performed using BET v2.1. Diffusion tensors are reconstructed using FSL's DTIFIT tool within the Diffusion Toolbox.

[figure not shown]
6.4.6 DTI Co-Registration with Same Subject's aMRI

[figure not shown]
FMRIB's Linear Image Registration Tool v5.5 (FLIRT) is used to perform co-registration between each subject's T1-weighted series and corresponding non-diffusion-weighted series from the DTI dataset. The resultant transformation matrix, and the calculation of its inverse, provides the basis for co-registering the tractography results (performed in diffusion space) and volumetric results (performed in T1 space). For group-level analyses, a study-specific template will be constructed within FSL by pooling and aligning the FA maps of all study participants using a non-linear registration algorithm included with FSL (FNIRT). Although FSL includes FA templates, these were generated from adult subjects and may introduce some error in our analyses of pediatric data.

6.4.7 Region of Interest and Fiber Tracking Analyses for DTI Data

Using FSL's ProbtrackX tool, probabilistic tractography methods are used for fiber tracking of major WM bundles. Combined use of color-coded tensor maps (Douek, Turner et al. 1991) generated by FSL's DTIFIT tool co-registered with the high resolution anatomy available in the T1-weighted series will facilitate tractography by utilizing the seed-to-mask feature in ProbtrackX where one mask is used as the seed mask and one or more masks are used as waypoints/targets. Such "masked-based" tractography reliably generates well-characterized tracts across study participants while preserving individual topology. In the ROI-based analyses FA values will be computed for major white matter bundles including three branches of the superior longitudinal fasciculus (SLF I, SLF II, SLF III) from the arcuate fasciculus [AF]), the corticospinal tract (CST), and the corpus callosum (CC). Using methods of tract delineations described by Catani (2008), Makris (2005), and Glasser (2008), Figures 7 A/B illustrates the AF with 3 branches of the SLF.

[figure not shown]
Figure 7 A

Figures 7 A/B: Integration of multi-modal imaging data. Cortical GM masks are displayed in a 3D viewer with results of mask-based tractography of the arcuatefasiculus. Separate branches of the SLF (e.g. I,II,III) are evident in distinct terminations in superior frontal (SLF I), middlefrontal (SLF II), and inferior frontal (SLF III) cortices. Panel on the right represents the same data with the cortical GM more transparent(s) to view the underlying tractography results. AF: lateral to cingulum bundle connecting posterior temporal (dark blue=bank of the superior temporal sulcus) with parietal (green=supramarginal) and frontal cortices; SLF I: branches into superior frontal (light blue); SLF II: branches into middle frontal (tan); SLF III: branches into inferior frontal (yellow).

For analysis of inter-hemispheric connectivity by the corpus callosum, Freesurfer-generated volumes as well as DTI measures of FA and MD from five subdivisions of the corpus callosum (e.g. anterior=pink, mid-anterior=green, central=yellow, mid-posterior=blue, and posterior=red) will be related to neurobehavioral assessments of function and outcome.

For investigating **motor networks**, Freesurfer-generated volumes of midbrain subcortical regions (e.g., thalamus and basal ganglia) will be related to measures of motor performance and processing speed.

Figure 9

[figure not shown]
[figure not shown]

Figure 9: Reconstruction of right cst using FSL's probabilistictractography methodology (red/yellow probability map) overlaid onto color-coded reconstruction of diffusion tensors (red=interhemispheric; blue=superior-inferior; green=anterior-posterior).

Additionally, Freesurfer-generated volumetric measures from primary motor cortex and DTI measures of FA and MD from the corticospinal tract (CST) will be related to neurobehavioral assessments of function and outcome.

To study language networks, Freesurfer-generated volumetric measures from inferior frontal regions (e.g. pars opercularis and pars triangularis in yellow), temporal regions (superior- and middle-temporal not shown), and parietal regions (e.g. supramarginal and angular in green) will be related to language measures. Furthermore, DTI measures of FA and MD from the same GM regions and the AF/SL (in red) will be related to neurobehavioral assessments of function and outcome (Figure 10).

Figure 10

[figure not shown]
6.4.8 MRI Quality Control Procedures

At the time of acquisition, we have procedures to check the aMRI and DTI data for outliers and confounding artifacts due to acquisition (e.g. image geometric distortions, field in homogeneity, signal-to-noise-ratio) and motion. If problems occur during scan acquisition, the sequence will be repeated to optimize image quality within the same imaging session based on real-time evaluation of imaging data and decisions made by [name]. All post-processing procedures of aMRI and DTI data include highly interactive protocols (i.e., not fully automated) requiring visual inspection of the data at each processing stage, which provides the best assurance of image quality. A standard water phantom will document and monitor scan quality at each imaging session. Post-processing procedures include quantitative evaluation of eddy currents and head movement using ExploreDTI v4.8.1 software provided by [name]. Evaluation of DTI data acquired from our living phantom in Houston is presented below in Figures 11 and 12. Our criteria for disqualifying DTI datasets and re-acquiring DTI data within the

same imaging session are translations greater than one voxel (e.g. 2 mm) or rotations greater than 1°.

Figure 11

Figures 11: Quantitative evaluation of DTI data quality using Explore DTI v 4.8.1. On the left, the percentage of outlier voxels is plotted as a function of diffusion-weighted gradient direction number and slice number. On the right, rotations, translations, scale, and skew are plotted for each cardinal plane as a function of diffusion-weighted direction number.

6.4.9 Secondary Imaging Outcome Measures & Correlation with Functional Outcome

As noted in the section, "CP Neuroimaging", cerebral palsy is a clinical diagnosis comprising a heterogeneous group of patients. This heterogeneity is manifest both in the dominant clinical symptom complex, but also in the imaging correlates of the symptoms. To that end, prior to treatment this study will quantify the degree of functional impairment (GFCMS level), and correlate it with the CP subtype and imaging abnormality. The imaging ROIs will be prospectively identified pre-treatment. Then, according to the qualitative and quantitative metrics, the imaging data will be recorded. Post-treatment, these same ROIs will be compared to the baseline data, and correlated with any changes in functional outcomes as measured by specific tasks on the GFCMS. Ultimately, the changes in WM and GM ROIs that are associated with CP will be compared with and without treatment using autologous bone marrow derived mononuclear cells or autologous cord blood mononuclear cells. These data will provide a structural metric around which future studies could be powered. Further, these data may provide potential mechanistic targets in terms of structural preservation and restoration in patients with CP.

7. MANAGEMENT OF ADVERSE EXPERIENCES

There are currently no neuroprotective/restorative treatments for CP in adults or children. Any potential risks must be weighed against the lack of treatment alternatives.

The majority of the risk related to the study is associated with the bone marrow harvest and infusion periods and are discussed in section 6.2.

7.1 Infection

There have been studies on complications of marrow harvest, and these studies note a 0.1-0.4% serious complication rate including: cellulitis at aspiration site, pneumonia and bacterial sepsis (Cairo, 1989; Jin, 1985; Kessinger, 1987). It is anticipated that the infectious risk will be lower than that reported in the oncology/BMT literature due to the relative immunocompetence of the CP population. We had no infections in our Phase I Trial. Parent(s)/LAR will receive detailed instructions at discharge regarding monitoring for signs of infection. There will be daily contact with the parent(s)/LAR for the first 21 days post-infusion for safety monitoring.

7.2 Other Harvest Related Issues

Bone marrow aspiration may cause discomfort. Hemorrhage, nerve injury and bone fracture are rare but reported complications that will monitored. Because the autologous BMMNCs used, are intravenously infused we do not anticipate any adverse reaction to them as may be occur in allogenic bone marrow transplants. Because this type of treatment has only been reported in head injured children in our Phase I trial, we may encounter other unexpected and unforeseen complications related to this treatment.

7.3 Psychological and Functional Outcome Testing

Subjects enrolled in the trial will be asked to take tests of memory, attention and motor skills. Parent(s)/LAR will be asked to fill out questionnaires that ask about the child's learning and behavior. Measures will be taken to minimize any stress participants may experience with testing procedures. All tests will be conducted in a private room located in the Outpatient Pediatric Surgery Clinic. Ample time will be given for completion of the tests.

7.4 Loss of Confidentiality

There is a potential risk of loss of confidentiality of subject information and data. All study related records will be stored in locked office and cabinets within the Dept. of Pediatric Surgery. Access to study records will be restricted to research team members, the study monitor, and UT IRB representatives. Case report forms will contain only the subject's study ID. The study database will reside within UTHealth Medical School, firewall protected, zone 100 servers. Assess to the study database will be limited to research team members.

8. CRITERIA FOR INTERVENTION DISCONTINUATION

8.1 Description of Subject Completion

Subjects are considered to have completed the study if they have undergone the BMMNC/hUCB infusion at either the baseline or the 1 year cross-over visit and have completed the 2 year end of study visit.

8.2 Withdrawal of Individual Subjects

The Principal Investigator will make every reasonable effort to keep each subject in the study through the 2 year visit. If a subject withdraws from the study, the reason for withdrawal must be documented in the study chart. Possible reasons for withdrawal include: adverse experiences, protocol deviation, including non-compliance, lost to follow-up, discretion of investigator or DSMB, or other regulatory agency/body. Subjects will be withdrawn from the study immediately if any of the following occur:

- a. The subject or their parent(s)/LAR requests withdrawal from the study.
- b. The investigator believes it is in the best interest of the subject.
- c. There is clinically significant deterioration of the subject's medical status that warrants termination from the study.
- d. There are clinically significant abnormal laboratory results that warrant termination from the study.

[figure not shown]
8.3 Withdrawal of Subject from the Study Following Adverse Events

The investigator must apply his clinical judgment to determine if an adverse event (AE) is of sufficient severity to require that the subject should immediately be withdrawn from the study. If the withdrawal from the study is due to an AE, the subject should be given appropriate care under medical supervision until the symptoms of the AE resolve or his/her condition becomes stable. Subsequent review by the MSM, DSMB, or IRB may also result in the suspension of further trial enrollment (see Stopping Rules). A subject (or Parent/LAR) may also voluntarily withdrawal from treatment due to what he/she perceives as an intolerable AE, or for any other reason. If voluntary withdraw is requested, or if withdrawal occurs for any reason, the subject should be asked to continue (at least limited) scheduled evaluations, complete an end-of-study evaluation, and be given appropriate care under medical supervision until the symptoms of any AE resolve or the subject's condition becomes stable.

8.4 Procedures for Handling Withdrawals

In case of early withdrawal, subjects will be asked to continue (at least limited) scheduled evaluations and to complete an end-of-study evaluation which includes all scheduled exams, procedures, and laboratory tests as if it is the 12 Month visit; and should be given appropriate care under medical supervision until the symptoms of any AE resolve or the subject's condition becomes stable. If the subject is unwilling or unable to complete visits, he/she will be asked to return for the end-of-study visit and then should be followed through telephone calls by the coordinator. Subjects who do not complete study treatment or all follow-up will be asked to provide the same data as subjects who withdraw.

8.5 Subject Replacement

Subjects will not be replaced once randomized.

9. STATISTICAL CONSIDERATIONS

9.1 Outcomes

9.1.1 Primary Safety Objective

Baseline characteristics of participants will be summarized using descriptive statistics and tabulations. Evaluation of data will be guided by exploratory analyses. All results will be reported as point estimates (percentages for binary outcomes and means \pm SD and median (range) for continuous outcomes) with corresponding interval estimates (two-sided 95% confidence intervals). No adjustments for multiple comparisons will be made and a p-value of 0.05 will be considered statistically significant.

These data are collected over time and will be longitudinal in nature with several predefined points of follow-up. We will use analytic strategies and methods applicable to such designs. For each participant in the cohort we have a set of "k" independent variables $\mathbf{x}' = (x_1, x_2, ..., x_k)$, of which some may be time varying (e.g., blood pressure) and others do not change over time (e.g., gender). In addition, the outcome variables of interest are also measured repeatedly over time (e.g., temperature, signs of infection, neurological exams, CBC, chem-20). We plan to explore any changes over time between hospital discharge and long-term follow-up at 6 months, 1 year, and 2 years after cell treatment with repeated measure model analyses. In this study, we plan to explore and identify potential factors associated with time to SAEs, AEs, death (refer to section 6.2), loss to follow-up (short term and long term), and improvements in functional outcomes (refer to section 6.3). We plan to explore the factors associated with the time to an event using survival analysis methods which incorporate information about the timing of withdrawals, deaths, and functional improvements (if any) of subjects during the follow up period. We plan to first use descriptive statistics to explore the characteristics of the subjects among events and then will use the Kaplan-Meier method to estimate the time to an event. Combined, these secondary analyses may provide useful preliminary estimates for the design of future cell studies.

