1.2 Secondary Objective

To determine if late functional outcomes are improved following the administration of autologous cells compared with subjects in the control group. Efficacy outcome measures:

- 1. aMRI volumetric white matter, grey matter, and CSF space volumes at Baseline, 1 year and 2 years post-treatment. Detailed volumetric analysis of the corpus callosum and white matter tract such as the corticospinal tract will be measured (fractional anisotropy and mean diffusivity) as well. Specific white matter tract analysis will be identified at baseline MRI and correlated with motor function studies as the primary lesion of interest. Total volumes and specific tract lesions will be analyzed and correlated with functional outcomes.
- 2. The following functional outcomes studies will be performed at baseline, 6 months, 1 year after infusion, and 2 year after infusion.
 - a. Gross Motor Function Measures
 - b. Psychological Assessment Batteries

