A large body of data indicates that both umbilical cord and bone marrow cells are attractive and highly promising sources of cell therapies for patients with brain injuries. The intravenous administration of mononuclear cells from umbilical cord and bone marrow has been shown in multiple animal models of cerebral ischemia to improve neurological outcome (Meier, 2006). A pilot study has already shown that autologous cord blood is safe to administer in infants with acquired neurological disorders (Sun, 2010). Pre-clinical and Phase 1 clinical studies have shown that BMMNC treatment for neurological injury reduces the neuro-inflammatory response and may preserve neural tissue. The precise mechanism of action and potential time-window of treatment has not been defined. Data in rodent models of stroke suggests that the 30-day time window may be the limit of potential effectiveness (de Vasconcelos dos Santos, 2010). In contrast, longitudinal imaging studies of patients after moderate TBI have shown progressive axonopathy, detectable by DTI in the regions of interest described above (callosal volumes, FA, MD) from the 2 week post-injury time point to 6 months postinjury (Kumar, 2009). This progressive, ongoing evolution of the imaging findings suggests progressive demyelination and gliosis (Kraus, 2007). Preservation of white matter volumes and callosal volumes correlate positively and significantly with neurocognitive outcome. Given the safety findings in our pediatric Phase 1 study, we have designed this study to use an imaging based/ structural outcome variable as our primary measure of efficacy.

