9.1.2 Secondary Objectives/Outcomes

The models proposed will be tested using general linear models (GLM). We will examine all variables to determine that they are relatively symmetric and unimodal, examine group variances for obvious deviations, and examine the residuals from each model to ensure reasonable adherence to the assumptions of normality and independence. If any variables violate the assumptions, we might transform skewed variables. We will evaluate the comparability of our groups on key demographic variables and will covary variables if necessary (e.g., socioeconomic status). For Efficacy Outcome Measure 1 (refer to section 1.2.1), we will use repeated measures ANOVA or ANCOVA (including intracranial volume as a covariate for macrostructure analyses) with Group (Treatment, Control) as the between-subjects factor and Time of Assessment (baseline, 1 year, and 2 years) and Age as the within-subjects factors. We

will examine the Age x Group x Time interaction and two-way interactions for each analysis and will trim non-significant terms from each model. If GM and WM volumes or DTI metrics vary across time, we will complete trend analysis to identify whether a linear or quadratic function best fits the data. Dependent variables will be evaluated in separate analyses. Dependent variables will be 1) the volume of whole brain gray matter, white matter, and CSF; 2) FA of core white matter pathways (corpus callosum, arcuate/superior longitudinal fasciculus), and 3) MD of gray matter in frontal and temporal cortical regions.

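### Section 2.2 declares a primary imaging measure of efficacy, but none is named, and at least seven imaging variables are each tested at an unadjusted 0.05

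*Combined protocol and SAP*

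**What the plan says.** - **Primary efficacy measure.** Section 2.2 (Pre-Clinical Data) ends: "we have designed this study to use an imaging based/ structural outcome variable as our primary measure of efficacy". The variable is not named there or anywhere else.
- **Objectives.** Section 1.1 makes safety the only primary objective. Section 1.2 puts efficacy second, and its first efficacy measure is a list that opens with "aMRI volumetric white matter, grey matter, and CSF space volumes at Baseline, 1 year and 2 years post-treatment" and goes on to callosal and tract measures. None is ranked above the others.
- **Sample size.** Section 3 ties the sample size to an effect on gray and white matter volumes together.
- **Models.** Section 9.1.2 names three sets of dependent variables: "the volume of whole brain gray matter, white matter, and CSF"; "FA of core white matter pathways (corpus callosum, arcuate/superior longitudinal fasciculus"); and mean diffusivity (MD) of frontal and temporal gray matter. It adds: "Dependent variables will be evaluated in separate analyses". Each model has Group, Time (baseline, 1 and 2 years) and Age. The three-way and two-way interactions are examined, and non-significant terms are then removed.
- **Threshold.** Section 9.1.1 says: "No adjustments for multiple comparisons will be made and a p-value of 0.05 will be considered statistically significant". This stands under the safety heading, but its paragraph covers all results and Section 9.1.2 sets no other threshold. The same paragraph promises "corresponding interval estimates (two-sided 95% confidence intervals").

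**The concern.** A threshold of 0.05 without adjustment can be defended in two situations: one test has been named in advance as the one that counts, or the p-values are openly descriptive. This plan does neither. It announces a primary efficacy measure, leaves it unnamed, and attaches the label of statistical significance to any result below 0.05.

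Three choices stay open: which variable, which visit, and which group term carries the efficacy question. The visit matters because, under Sections 5.1.8 and 5.2.10, the blind is broken ahead of the 1-year visit and sham children may then receive cells. A 1-year contrast and a 2-year contrast therefore answer different questions. At stake is whether a result labelled significant in 30 children has any stated error rate behind it.

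**Working it through.** **The plan's own figure.** The only error rate in the documents is 0.05 per test. For one named test the chance of a false positive is 1 − 0.95 = 5%. No error rate is given for the set of tests.

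**Inputs from the documents**
- Variables (Section 9.1.2): gray matter, white matter and CSF volume (3); fractional anisotropy (FA) of the corpus callosum and of the arcuate/superior longitudinal fasciculus (2); MD of frontal and of temporal cortex (2). Total 3 + 2 + 2 = 7, a minimum.
- Group terms per model (Section 9.1.2): Group, Group × Time, Group × Age and Age × Group × Time, so up to 4.
- Threshold (Section 9.1.1): 0.05, unadjusted. Intervals are two-sided, and tests are taken as two-sided.
- Size (Section 3): 30 children allocated 2:1, so about 20 treated and 10 sham.

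**Independent tests, no effect.** The chance of at least one p < 0.05 among k tests is 1 − 0.95^k, and the expected number is 0.05k.

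| Terms counted | k | Chance of at least one | Expected number |
|---|---|---|---|
| Group × Time only | 7 × 1 = 7 | 1 − 0.698 = 30.2% | 0.35 |
| Group × Time and Age × Group × Time | 7 × 2 = 14 | 1 − 0.488 = 51.2% | 0.70 |
| All four group terms | 7 × 4 = 28 | 1 − 0.238 = 76.2% | 1.40 |

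**Correlated outcomes.** Brain measures on the same child are correlated, which lowers these figures. The documents give no correlation, so a range is assumed. Null data were simulated 20,000 times per correlation value with 20 against 10 children, three visits and a within-child correlation of 0.8 (assumed). Age was a between-child covariate, and the full model was kept without removing terms.

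| Correlation between outcomes | Any of 7 Group × Time tests | Any of 28 group terms |
|---|---|---|
| 0 | 30% | 76% |
| 0.3 | 28% | 72% |
| 0.5 | 23% | 65% |
| 0.7 | 19% | 55% |
| 0.9 | 12% | 39% |

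The 14-test case was not simulated; positive correlation would bring it below 51%. Removing non-significant terms was not simulated either.

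**The case against.** **The plan is an early-phase safety study and says so.** Safety is the only primary objective, Section 9.2 sizes the trial as a safety study, and Section 9.1.1 calls its evaluation exploratory and aimed at planning later trials. The lack of adjustment is disclosed, and estimates with 95% intervals are already promised. All of this stands and lowers the severity. It does not settle the matter, because the same paragraph still declares a significance threshold and Section 2.2 still declares a primary efficacy measure.

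**Section 2.2 is background prose.** Its wording can be read as the type of outcome (structural rather than functional) and not as exactly one variable. That is fair. On either reading it has to be reconciled with Sections 1.2 and 9.1.2, which contain no primary efficacy measure.

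**Some choices are fixed in advance.** Section 6.4.9 has regions of interest identified before treatment, and Section 1.2 identifies tracts of interest on the baseline MRI. This is real partial pre-specification, so the choice is not wholly free. It still does not fix one group-level endpoint, visit or contrast.

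**Stronger readings that a reader might infer:**
- *A significant efficacy result is likely by chance.* This depends on what is counted. One Group × Time test per variable gives about 23–30% at correlations up to 0.5. A figure well above one half needs all 28 terms, and two of the four terms are weak tests of efficacy: the Group main effect averages in baseline, and Group × Age is not a change over time.
- *The correlations in the second part of Section 9.1.2 should be added to the count.* They relate brain measures to behavior and are not treatment contrasts. The plan expects them to be non-zero, so a significant one is not a false claim of a cell effect.
- *The callosal subdivisions in Section 6.4.7 multiply the tests.* That section relates them to neurobehavioral measures, not to a group comparison.
- *A chance finding will be presented as proof that the cells work.* No section says so.

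**Conclusion.** The point holds as a gap in specification with a moderate, calculable consequence. A primary imaging measure of efficacy is announced but not identified, and the significance label applies to every one of at least seven separately modelled variables. With no effect, the chance of at least one significant Group × Time result is 30% under independence and about 23% at an outcome correlation of 0.5, roughly five to six times the nominal 5%. Under independence it is 51% for 14 tests and 76% for 28, the latter falling to about 39% at correlation 0.9. The size rests on the assumed correlation and on which group terms count as efficacy tests, which the plan leaves open. Because efficacy is secondary and largely exploratory, this should be corrected, but it does not threaten the primary safety objective.

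**What to change.** Either of two changes resolves it.

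1. Before unblinding, the sponsor names one imaging variable, one time point and one group contrast in Sections 1.2 and 9.1.2, and reserves the 0.05 test for that contrast. All other efficacy results are reported as estimates with 95% confidence intervals and no claim of significance. The single test then carries 5% and needs no adjustment. The choice of variable is the sponsor's; Section 3 points equally to gray and white matter volume. Because the blind is broken ahead of the 1-year visit, the choice must in practice be fixed before anyone sees imaging results by group.
2. Alternatively, the sponsor corrects Section 2.2 to say that there is no primary efficacy variable, and labels all p-values in Section 9.1.2 exploratory.

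Both are wording changes, with no added children, visits or scans. The cost is that efficacy results other than a named one can no longer be called significant; under the second option, none can.
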